v3.0	27 OCT 2021	Data management platform was changed to AirTable to increase security and ease of use. Option for study team to obtain verbal consent was added.
v4.0	30 NOV 2021	Broadened language to allow flexibility in testing frequency and time points based on evaluation of safety data (e.g. tertiary transmission) and feedback from the study safety committee and NCDHHS. Updated consent forms to reflect the protocol modifications.

PROTOCOL SYNOPSIS

Protocol Title:	Test to Stay in School: COVID-19 Testing Following Exposure in K-12 School Communities
NCT #	NCT05052580
Phase:	N/A, a prospective, interventional study
Objectives:	
Primary:
 
 1. Evaluate severe acute respiratory syndrome coronavirus 2 (SARS-CoV-2) transmission following exposure in Kindergarten through 12th grade schools. 
Secondary:
 
 1. Characterize the effect of individual-level mitigation practice (e.g., masking) on SARS-CoV-2 spread. 2. Characterize the effect of exposure setting on SARS-CoV-2 spread. 3. Describe COVID-19-related school absences for up to 14 days following within-school SARS-CoV-2 exposure.
Study Design:	
Participants in school communities who have been exposed to SARS-CoV-2 will be tested for COVID-19 on the day after exposure (day 1) and at days 3, 5, and 7 following initial known exposure. Data will be reviewed weekly by a study safety committee and NCDHHS, and updates to the testing protocol (test frequency and test time points) will be made based on analysis of data. Mitigation practices including masking, the context of exposure (classroom, school bus, after school sporting event, lunch, etc.), and results of COVID-19 test will be documented.

Study Population:	School communities
Number of Participants:	Up to 1,000,000
Number of Sites:	Single coordinating site
Duration of Study:	2 years

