1 BACKGROUND INFORMATION AND RATIONALE

1.1 Background Information

1.1.1 COVID-19 and Kindergarten-12th grade school closures

Widespread Kindergarten through 12th grade school closures are the most important COVID-19-related threats to child health. Since February 2020, children have accounted for one-tenth of severe acute respiratory syndrome coronavirus 2 (SARS-CoV-2) cases; up to 2.2% and 0.04% of pediatric cases have resulted in hospitalization or death, respectively, and as many as 50% of cases are asymptomatic.^{1,2} However, children have been far from spared of the downstream effects of this pandemic. In March 2020, most Kindergarten through 12th grade schools preemptively closed to in-person education in an attempt to limit viral spread. Most publically-funded Kindergarten through 12th grade schools across the nation, responsible for educating >55 million of the nation's children, remained closed in the early 2020, citing concerns about viral transmission and risks to students and staff. Because public schools play such a vital role in the educational, social, and emotional development of young children as well as the delivery of vital services such as food and healthcare, it is not surprising that early data show food insecurity has doubled; 65% of children 9-13 years are less physically active; 1/6th of children have worsened behavioral health; suicidality may be increasing, and physical abuse is more severe.³⁻⁷ The potential consequences of these findings are deep and far-reaching; children with food insecurity are twice as likely to be in fair or poor health, more likely to be hospitalized, and more likely as adults to have poor job readiness. Chronic absenteeism in early primary school decreases the likelihood of reading at grade level by the third grade and increases the risk of drop out by 4 times compared to proficient readers.⁸ Adults with less than a high school education are 2.4 times as likely as high school graduates to rate their health as poor and live 10 years fewer than those with graduate education. Considering these profound impacts, access to in-person education is imperative.

In North Carolina (NC), schools have been able to show low secondary transmission of SARS-CoV-2 within school buildings.⁹ Data in school communities confirms that mitigation strategies such as proper masking have been imperative in reducing spread in schools.⁹⁻¹¹

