5.5 Follow-Up

Participants will be asked to report symptoms for up to 14 days following SARS-CoV-2 exposure. Schools will be asked to report tertiary spread and number of close contacts for individuals who tested positive.

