8 STATISTICAL CONSIDERATIONS

8.1 Study Endpoints

8.1.1 Primary Endpoints

Primary Objective: Evaluate severe acute respiratory syndrome coronavirus 2 (SARS-CoV-2) transmission following exposure in Kindergarten through 12th grade schools.

Primary Endpoints:

- Proportion and number of students with positive COVID-19 test following known within-school exposure.
- Proportion and number of staff with positive COVID-19 tests following known within-school exposure.
- Proportion and number of exposures undergoing the test-to-stay protocol that result in additional (tertiary) transmission.
- Time to test positivity among those exposed to SARS-CoV-2 and undergoing the test-to-stay protocol.

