1.3 Endpoints

Primary Endpoints:

- Proportion of students with positive COVID-19 test following known within-school exposure.
- Proportion of staff with positive COVID-19 tests following known within-school exposure.
- Proportion of exposures undergoing the test-to-stay protocol that result in additional transmission.
- Time to test positivity among those exposed to SARS-CoV-2 and undergoing the test-to-stay protocol.

Secondary Endpoints:

- Secondary #1
 - Proportion of students with positive COVID-19 test following known within-school exposure.
 - Proportion of staff with positive COVID-19 tests following known within-school exposure.
 - Proportion of exposures undergoing the test-to-stay protocol that result in additional transmission.
 - Time to test positivity among those exposed to SARS-CoV-2 and undergoing the test-to-stay protocol.
- Secondary #2
 - Proportion of students with positive COVID-19 test after indoor vs. outdoor exposure.
 - Proportion of students with positive COVID-19 test after athletic vs. classroom exposure.
 - Proportion of students with positive COVID-19 test after bus vs. classroom exposure.
- Secondary #3
 - Total number of school days missed due to symptoms after exposure.
 - Total number of school days missed due to isolation after positive COVID-19 test.
 - Total number of school days missed due to quarantine after SARS-CoV-2 exposure.

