1.4 Handling of Missing Date

For any partially or completely missing date of testing, the scheduled testing day (Day 1, 3, 5, 7) will be used for days to test positivity.

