3.4 Endpoints

Primary Efficacy Endpoints:

- Days of in-school work and education saved, defined as the number of days a participant could attend in-person work or learning after being notified of a household member who tested positive for SARS-CoV-2.

Safety Endpoints:

- Primary: Tertiary attack rate (TAR) or within-school transmission of SARS-CoV-2, defined as the rate of transmission to within-school close contacts of positive TTS participants
- Secondary: Secondary attack rate (SAR), defined as rate of transmission or test positivity among TTS participants

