3.5 Handling of Missing Data

No imputation will be performed; Missing data will be excluded from all denominators.

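### In the protocol and SAP Manuscripts 1 and 3, tertiary transmission rests on school reports with no specified count of contacts tested, so under-detection is likely and cannot be measured

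*Protocol*

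**What the plan says.** - **Ascertainment.** Protocol 5.5 gives the only stated method: "Schools will be asked to report tertiary spread and number of close contacts for individuals who tested positive". The schedule in Protocol 5.1 provides testing for participants only.
- **Per-exposure endpoint.** Protocol 8.1.1 lists among four primary endpoints: "Proportion and number of exposures undergoing the test-to-stay protocol that result in additional (tertiary) transmission". SAP 1.3 (Manuscript 1) carries it over: "Proportion of exposures undergoing the test-to-stay protocol that result in additional transmission". Neither sets a condition on how contacts were ascertained.
- **Per-contact rate.** SAP 3.4 (Manuscript 3) makes the tertiary attack rate (TAR) its primary safety endpoint, "defined as the rate of transmission to within-school close contacts of positive TTS participants". It sets no enrolment or testing condition on the contacts.
- **Missing data.** SAP 1.4 deals only with dates: "For any partially or completely missing date of testing, the scheduled testing day (Day 1, 3, 5, 7) will be used". SAP 3.5 says: "Missing data will be excluded from all denominators". It does not say whether an untested contact is missing or a non-case.
- **Manuscript 2 differs.** SAP 2.4 limits TAR to contacts who themselves enrolled in Test to Stay, and SAP 2.3 requires at least one valid test result for enrolment.
- **Use of the measure.** The version 4.0 entry in the protocol's history of changes allows flexible testing frequency "based on evaluation of safety data (e.g. tertiary transmission" being the example given). Protocol 3.1 and 5.4 allow fewer tests if the data are judged to show this is safe.

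**The concern.** A case count and a contact count give a rate only if every contact had a fair chance of being found positive. Nothing in the plan secures that. Under Protocol 3.2, people enrol and test in order to avoid quarantine. Protocol 1.1.1 says quarantine had been dropped for most masked children exposed to a masked child in class. Manuscript 3 draws on universally masked schools (SAP 3.2), so some of its tertiary contacts may have had no reason to test.

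A low rate could then reflect little testing as well as little transmission, and the reported data would not tell the two apart. Because tertiary transmission informs decisions about testing frequency, under-detection would favour a finding of safety. For participants, the SAP does not accept the mere absence of a positive as a negative: SAP 2.3 and 3.3 require a positive test or a sufficiently late negative one. Tertiary contacts in Manuscripts 1 and 3 have no equivalent requirement.

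**Working it through.** The documents give no tertiary rate, no share of contacts tested and no number of contacts per positive participant. There is no planned figure to reproduce.

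**Step 1: follow an untested contact through each definition.**

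- *Manuscript 3.* The school supplies k tertiary cases and C close contacts, so the available rate is k/C. An untested contact adds 1 to C and nothing to k, unless found some other way. Applying SAP 3.5 would need the number of contacts with an outcome, which C does not show.
- *Protocol and Manuscript 1.* If none of a positive participant's contacts was tested, there may be nothing to report, and the exposure stays in the denominator as transmission-free. No rule sets it to missing. Exposures whose participant never tested positive are unaffected.
- *Manuscript 2.* An untested contact is outside the rate, so this mechanism is absent.

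**Step 2: illustrate the size.** Inputs:

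- a, the asymptomatic share: 0.5 from Protocol 1.1.1 ("as many as 50% of cases are asymptomatic", an upper figure for pediatric cases), with 0.25 as an assumed alternative.
- p, the share of contacts tested regardless of symptoms: assumed.
- T, the true TAR: assumed 1%.

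Assume an untested infected contact is found if and only if symptomatic. Then

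reported/true = p + (1 − p)(1 − a) = 1 − a(1 − p), which is 0.5 + 0.5p at a = 0.5.

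For a rate over tested contacts only, assume also that those found through symptoms have a test result and that no uninfected contact tests because of symptoms. With f = reported/true,

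tested-only rate = T·f / [T·f + (1 − T)·p].

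At p = 0.5 this is 0.0075 / (0.0075 + 0.495) = 1.49%.

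| p | f, a = 0.5 | f, a = 0.25 | All-contacts rate (T = 1%, a = 0.5) | Tested-only rate (T = 1%, a = 0.5) |
|---|---|---|---|---|
| 0 | 0.50 | 0.75 | 0.50% | not informative |
| 0.1 | 0.55 | 0.775 | 0.55% | 5.3% |
| 0.5 | 0.75 | 0.875 | 0.75% | 1.49% |
| 0.9 | 0.95 | 0.975 | 0.95% | 1.05% |

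Read backwards at a = 0.5, a reported 1% corresponds to a true rate between 1/0.95 = 1.05% (p = 0.9) and 1/0.50 = 2% (p = 0).

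**Step 3: a harsher assumption.** If untested infections are never found, and testing is unrelated to infection, reported/true equals the share tested, q. A true 5% appears as 1.5%, 2.5%, 3.5% or 4.5% at q = 30%, 50%, 70% or 90%. Per exposure with a positive participant and five independent contacts (assumed), the true proportion is 1 − 0.95^5 = 22.6%. The observed one, 1 − (1 − 0.05q)^5, is 7.3%, 11.9% or 16.3% at q = 30%, 50% or 70%. Exposures without a positive participant add nothing to either numerator, so the ratios (0.32, 0.53, 0.72) also hold over all exposures.

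**Step 4: what could offset it.** Let a further share c of tested contacts have community infections counted as tertiary. Under Step 3 the bias cancels when q(T + c) = T, so c = T/q − T. At T = 5% and q = 50%, c = 5%.

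**The case against.** - **The documents do not say an untested contact is a non-case.** This is correct. A reader might infer a stated rule, but it is a consequence drawn from silence. The SAP's written rules remove missing values from denominators (General Statistics Principles, worded for participants; SAP 2.5 and 3.5). They do not rescue the school-reported rate, because a contact count does not identify who lacks an outcome.
- **The count may exist.** The spreadsheet and AirTable fields are not in the documents, Protocol 13.4 allows extra school data at individual level, and contacts who enrol have results in the study's own data. So the supportable statement is that the count is not specified. The documents do not show that it is not collected.
- **Many contacts had reason to test.** Protocol 1.1.1 adds that quarantines continued for unvaccinated adults, children exposed to infected adults, and masked exposures outside class, and rose as mask mandates were lifted. This stands: the share tested is unknown and could be high.
- **The net direction is not fixed.** No criterion separates within-school from community infection, and Step 4 shows that misattribution could cancel the shortfall. This bars the claim that the rate is certainly too low. It is a second unmeasured error and does not remove the first.
- **A tested-only rate may be worse.** In Step 2 it is 1.49% or 5.3% against a true 1%, where the all-contacts rate is 0.75% or 0.55%. This stands, and is why the tested-only rate should not replace the other.
- **Tertiary transmission might be read as the trial's main safety measure.** Only SAP 3.4 gives it that rank, for Manuscript 3. Protocol 6 limits safety events to swab effects, and the history of changes names tertiary transmission only as an example of safety data.

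**Conclusion.** The point holds for the protocol endpoint and SAP Manuscripts 1 and 3. As written, an untested contact, or an exposure whose positive participant had no tested contact, in effect enters as no transmission. Under-detection is likely, and the specified data do not allow it to be measured or corrected.

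The size is illustrative: a ratio of reported to true of 0.50 to 0.95 for p from 0 to 0.9 at 50% asymptomatic, and 0.75 to 0.975 at an assumed 25%. This rests on an assumed p, on every symptomatic untested case being found, and on a pediatric upper figure applied to contacts who include staff.

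A reader might go further and conclude that the trial's tertiary rates are all biased low. The documents do not support that: Manuscript 2 uses enrolled, tested contacts, and community infections counted as tertiary could push the other rates up.

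**What to change.** - **Protocol 5.5:** for each positive participant, add to the school report the number of close contacts with at least one known test result after the contact. This asks for a count and requires no additional testing.
- **SAP 1.5 and 3.6:** report tertiary transmission over all close contacts, labelled as likely under-detecting, and over tested contacts, labelled as likely too high if symptomatic contacts test more. Present the two as a range. Neither is a strict bound, given possible misattribution, and neither replaces the other.
- **Per-exposure endpoint:** show separately the exposures whose positive participant had no tested contact, and do not merge them with exposures that had no transmission.
- **Safety committee:** supply both figures.
- **Data already collected without the count:** state that contact testing is unknown and label the all-contacts rate accordingly. This probably applies to Manuscript 3, whose exposures ran from 1/8/22 to 2/15/22 (SAP 3.3) and whose SAP section is dated June 14, 2022. If the count can be recovered from existing records, use it.

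The cost is one more number in the spreadsheet or AirTable and one more table column. The count will be incomplete for some schools, which may not know the test results of contacts who never enrolled, and the tested-only rate will rest on fewer contacts.

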6 ASSESSMENT OF SAFETY

Participants will be asked to self-report safety events related to testing and after each testing event on pre-specified testing days. Because these tests have undergone rigorous safety assessments, this study will only collect safety events related to known testing procedures risks, which include nose irritation, local pain around nose, and nose bleeding. Serious and unanticipated safety events are not expected to occur in this study and therefore no expedited safety reporting will occur. Participants will be provided with contact information if they experience any concerning safety events and wish to report them outside of the study safety assessment survey. The study principal investigator will review aggregate safety information and determine if any of the safety information requires Institutional Review Board (IRB) submission and review according to Duke University Health System (DUHS) IRB reporting policies.

7 Study Termination

This study may be terminated at any time by the funding agency or the study principal investigators. Reasons for termination may include but are not limited to, if in their judgment, there are no further benefits to be achieved from the study. If the study is terminated, notifications will be made to the IRB of record and study participants, in accordance with all applicable regulations governing the study and site/investigator.

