Yet, current policies and procedures requiring quarantine after close contact exposures to limit further spread have led to hundreds of thousands of missed school days and have threatened the school workforce, greatly impeding school operations and the ability of children to appropriately learn. In the fourth quarter of 2021 in NC alone, more than 40,000 students and staff were required to quarantine as a result of being a close contact of a COVID-19 case (unpublished). Fortunately, recent CDC and local guidance have eliminated quarantines for most exposed, unvaccinated, asymptomatic children who are wearing a mask and who are in close contact with another masked, infected child within the classroom setting. However, many quarantines continue to result in unvaccinated adults, children exposed to infected adults, and masked exposures occurring outside of the classroom (e.g., athletics or busing). Moreover, schools and local governments are steadily lifting mask mandates, even as local community cases rise, contributing to exponential increases in quarantines that not only keep children and staff out of schools and parents out of work, but have often overwhelmed school resources and the public health system.

To address the issue of quarantines while ensuring that the school and surrounding community remain safe from SARS-CoV-2 spread, some locales have begun implementing a "test to stay strategy", whereby a close contact undergoes serial testing over a specified duration of time.

The close contact must wear a mask during this time period but is not required to undergo quarantine as long as the screening tests remain negative and the contact remains asymptomatic. While this strategy is supported by strong scientific premise and initial data are promising, the impact of this strategy on quarantine, and secondary and tertiary within-school transmission has not been systematically evaluated.

This study will partner with schools to allow students and staff to remain in school following exposure if they continue to test negative for COVID-19 over pre-determined intervals. This study aims to collect data to assess the spread of SARS-CoV-2 in school communities with varying mitigation strategies to provide data-backed guidelines for mitigation strategies in schools. The study team will work with NCDHHS and a safety monitoring team on a weekly basis to interpret data, evaluate safety, and design next steps (e.g. testing frequency and timing).

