1.4 Known Potential Risks

Community-level risk(s): For school communities to participate in this protocol, there is a potential risk for increased exposure to SARS-CoV-2 from elimination of quarantine; however,

frequent testing, symptom screening and requirements for masking in a controlled environment are designed to minimize this risk to the community.

Individual-level risk(s): Risks associated with this study include risks associated with the COVID-19 testing procedure, specifically risks associated with lower nasal swab and the potential loss of confidentiality.

- **Potential Risks of Nasal Swabs:** Risks include mild irritation, insignificant local pain, and minor bleeding.
- **Potential Risk of Loss of Confidentiality:** There is a potential risk of loss of confidentiality. Every effort will be made to protect the participant's protected health information (PHI) as well as other identifying information, but this cannot be guaranteed.

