8.3 Sample Size Considerations

No formal sample size calculation was completed for this study. This study will enroll up to 1,000,000 participants.

9 Future Use of Study Records

The research data collected in this study, and provided to the sponsor, will be kept indefinitely.

Information about this study, including study results, will be published without further permission from the participant as detailed in the informed consent form. Participants will not be identified in any publications or presentations made about the study.

After the study is completed, information about the study, including study data, may be provided to the National Institutes of Health (NIH). Identifiable data will be kept at the DCRI and the DCRI will not share these data with the NIH. With NIH approval, the data submitted may be used by other researchers for future research. The study data submitted will be de-identified, meaning it will not include any information that can identify the participant. The study team may also share the de-identified study data with other researchers. When the participant's de-identified study data are provided to other researchers for the purposes of future research, it will be done without obtaining additional permission.

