3.7 Sensitivity Analysis

- Objective: Repeat the main analyses among study participants who had a positive test on or after the day of exposure.
- Objective: Broaden primary analysis for considered positives that include presumed positives, defined as those who developed symptoms but did not receive a subsequent negative test.
- Objective: Estimate range of household SAR by using positivity reported in published literature. For individuals who were tested on day 9 or later, we will use existing TTS data. For participants who did not receive a test on day 9 or later, we will impute values to obtain a range, with the following visual representation as a plot:
 - SAR for the analysis eligible pop
 - SAR for the analysis eligible pop + presumed positives
 - SAR for the analysis eligible pop + presumed positives + 25% of the people with missing data as positive
 - SAR for the analysis eligible pop + presumed positives + 40% of the people with missing data as positive
 - SAR for the analysis eligible pop + presumed positives + 55% of the people with missing data as positive

→ Rationale, reports of SAR in household close contacts range from 25-55% positive. We would like to use published literature to give a range based on our existing data.

→ To account for the within-school correlation of outcomes, the 95% confidence interval (CI) for the proportion was estimated using an over dispersed binomial regression model. For sparse data, confidence intervals for SAR estimates were computed using the Clopper-Pearson approach.

→ The study team decided not to include to the manuscript.

References

Zeger SL, Liang K-Y, Albert PS. Models for Longitudinal Data: A Generalized Estimating Equation Approach. *Biometrics*. 1988;44(4):1049-1060.

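### The protocol tracks transmission, but Section 6 covers only swab effects, and hospitalisation or death from COVID-19 among positives is not systematically collected

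*Protocol*

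**What the plan says.** Protocol Section 6 sets the scope of safety collection: "this study will only collect safety events related to known testing procedures risks, which include nose irritation, local pain around nose, and nose bleeding". It justifies this by the safety assessments the tests have already passed. On reporting it says: "Serious and unanticipated safety events are not expected to occur in this study and therefore no expedited safety reporting will occur". Participants are given contact details for raising concerns outside the survey, and the principal investigator reviews safety information in aggregate and decides what goes to the IRB.

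Other sections bear on the same point:

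- Protocol 1.4, on the community: "there is a potential risk for increased exposure to SARS-CoV-2 from elimination of quarantine". Swab effects and loss of confidentiality are listed separately as individual-level risks.
- Protocol 1.1.1, on severity: "up to 2.2% and 0.04% of pediatric cases have resulted in hospitalization or death, respectively".
- Protocol 1.1.1, on oversight: "The study team will work with NCDHHS and a safety monitoring team on a weekly basis to interpret data, evaluate safety". Sections 3.1 and 5.4 allow the number and timing of tests to change if this is judged safe.
- Protocol 8.1.1 makes tertiary transmission a primary endpoint, and 5.5 asks schools to report it. The history entry for version 4.0 gives tertiary transmission as an example of safety data. SAP 3.4 lists the tertiary attack rate as the primary safety endpoint for the household cohort.
- The schedule in Protocol 5.1 marks Safety Assessment for the testing period only.

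**The concern.** The stated reason for collecting so little is that the swab tests are well characterised. That is a sound argument about swabs. It says nothing about the intervention, which is letting exposed people attend school rather than quarantine. Section 6 does not mention the community risk in 1.4, nor does it point to the transmission monitoring set out elsewhere.

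That monitoring counts infections; no item says how ill anyone became. The protocol allows testing to be reduced on the strength of the safety data, so the severity of resulting COVID-19 is relevant to that decision. If nobody asks about hospitalisation or death, a final report with no serious events could be read as evidence of safety when it may only reflect that the question was not put.

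**Working it through.** The documents give no expected number of serious events and no sample-size or power calculation, so there is no plan figure to reproduce. The check sets the sections side by side and then asks how many positives make a hospitalisation foreseeable.

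**1. Which named risks are followed, and how**

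| Risk in Protocol 1.4 | Where followed | What is recorded |
|---|---|---|
| Swab effects | Section 6; 5.1, testing period | Irritation, pain, bleeding |
| Added exposure in the school | 3.1, 5.5, 8.1.1, 8.1.2; SAP 3.4 | Tertiary spread, number of close contacts, symptoms to day 14, school days missed |
| Severity of resulting COVID-19 | No item in 5.1, 5.5 or 13.4 | Not systematically recorded |

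Timing widens the gap. Safety questions follow each test. Under Protocol 3.3, an entry explaining that testing stopped, for example because of a positive result, counts as completion. The structured safety prompts can therefore end at the positive test, although symptoms are to be reported up to day 14.

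**2. Positives needed for a hospitalisation to be foreseeable**

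Inputs from Protocol 1.1.1, both upper bounds for children: hospitalisation h = 0.022, death d = 0.0004.

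- One expected hospitalisation: 1/h = 1/0.022 = 45.5, about 46 positives.
- A 95% chance of at least one: ln(0.05)/ln(1 − 0.022) = 134.7, about 135 positives.
- One expected death: 1/d = 1/0.0004 = 2,500 positives.

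Because h is an upper bound, assumed lower values are shown too: h = 0.01 needs 100 positives, 0.005 needs 200, and 0.001 needs 1,000.

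**3. The part that staying in school could add**

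Only tertiary cases reflect the risk in 1.4. The documents give neither a tertiary rate nor a planning value for within-school positivity. Assumed ranges: 1% to 5% of participants positive, and 0.01 to 0.10 tertiary cases per positive.

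- Positives per expected tertiary hospitalisation: 45.5/0.10 = 455 to 45.5/0.01 = 4,550.
- 10,000 participants: 100 to 500 positives, 1 to 50 tertiary cases, × 0.022 = 0.02 to 1.1 hospitalisations.
- The ceiling of 1,000,000 (Protocol 8.3): 10,000 to 50,000 positives, 100 to 5,000 tertiary cases, × 0.022 = 2.2 to 110 hospitalisations.

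Among all positives at 10,000 participants, the same positivity range gives up to 100 × 0.022 = 2.2 to 500 × 0.022 = 11 hospitalisations. Most of those infections would come from the index exposure.

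**The case against.** The strongest reply is that the risk in 1.4 is worded as exposure, and exposure is what the study measures. Tertiary transmission is the direct measure, it is a primary endpoint, and schedule changes need both the safety committee and NCDHHS to judge them safe. This stands. The first risk in 1.4 is not ignored; the gap is confined to severity.

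Four stronger readings are tempting, and the documents do not support them.

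- *Section 6 contradicts 1.1.1.* The sentence concerns events that are both serious and unanticipated, and it follows text on test procedures. Hospitalisation after a known exposure is serious but can be anticipated, so both statements can be true. What remains is that Section 6 gives no specific route for anticipated serious outcomes.
- *The committee and NCDHHS see no severity data.* No section lists what they receive. Symptoms and missed days are collected and are crude indicators.
- *A hospitalised child would go unrecorded and unescalated.* Participants may report concerns, and the principal investigator may take matters to the IRB. The route is voluntary, however, has no denominator, and offers nothing explicit to a tertiary case who is not enrolled.
- *The household cohort shows hospitalisations caused by test-to-stay.* SAP 3.3 gives 322 enrolled, and SAP 3.7 says "reports of SAR in household close contacts range from 25-55% positive". Then 322 × 0.25 = 80.5 and 322 × 0.55 = 177.1 positives, × 0.022 = up to 1.8 to 3.9 hospitalisations. These people were exposed at home, so most of these events would occur with or without the programme. The range comes from the literature and was meant for imputing missing results, in a sensitivity analysis that the SAP says was left out of the manuscript. The cohort also includes staff, whereas 2.2% is paediatric.

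**Conclusion.** The concern holds in a limited form. Transmission is watched as safety data, but its clinical consequence is not systematically collected, and Section 6 gives a reason that fits the tests and not the intervention.

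The size is best stated as the break-even of about 46 paediatric positives per expected hospitalisation, at most. It rests only on the protocol's upper figure; no adult figure is given for staff. The attributable number depends on an undocumented tertiary rate and could be well below one in a study of 10,000. The products at 1,000,000 are ceilings multiplied by assumptions and should not be read as forecasts. The case for change does not depend on large counts: a hospitalisation among positives is foreseeable at modest scale, and the cost of asking is low. This is a worthwhile improvement to safety collection. It does not affect the validity of the transmission estimates.

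**What to change.** 1. In Section 6, reconcile the sentence on serious events with 1.1.1 and 1.4: limit it to test-procedure events, and cross-refer to tertiary transmission as safety data.
2. Add one yes/no item, hospitalised or died from COVID-19, for each consented participant who tests positive, including tertiary close contacts who enrol. Enter it in the existing AirTable or spreadsheet, and extend the Safety Assessment row in 5.1 to the follow-up column.
3. Put the running count into the weekly review by the safety committee and NCDHHS and into the principal investigator's assessment of IRB reportability. The sponsor and IRB should set the reporting rule.

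For tertiary cases who are not enrolled, use only de-identified aggregate counts, and only if schools already hold them. Individual collection there would raise consent and privacy questions.

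The cost is a short amendment and one data field; the testing schedule does not change. School staff already hold the key linking IDs to names, so the study team need not see identifiers. Section 12.1 may require updated consent forms. School-reported severity will be incomplete, a person positive on day 7 has only 7 days left to day 14, and many recorded events will be unrelated to test-to-stay.
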